2.6.3 Handling of missing values/censoring/discontinuations

Missing data will not be imputed for the primary efficacy analysis. Hence, the analysis of the primary variable is only conducted for patients with a non-missing value of VA at the patient's fifth birthday visit.

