2.2.1.1 Baseline definition and post-baseline definitions

All data collected after Day 1 of the Core study are defined as post-Core baseline.

All data collected after the Extension baseline visit are defined as post-Extension baseline. The study day relative to Core baseline for a scheduled or unscheduled visit which is on or after the date of first study treatment (of the Core study) in either eye is defined as

$$\text{Study day} = (\text{Date of visit}) - (\text{date of first study treatment in either eye in Core study}) + 1$$

The study day relative to Core baseline for a scheduled or unscheduled visit which is before the date of first study treatment (of the Core study) in either eye is defined as

$$\text{Study day} = (\text{Date of visit}) - (\text{date of first study treatment in either eye in Core study})$$

The study day relative to Extension baseline for a scheduled or unscheduled visit on or after Extension baseline is defined as

$$\text{Study day} = (\text{Date of visit}) - (\text{date of Visit 201 in Extension study}) + 1$$

For the purposes of classifying an eye by ROP disease status, the worst disease present in any clock hour of the eye, ranked in descending order from worse to best in [Table 2-1](#), will be used to classify the eye at Core baseline and during the study.

Plus disease is defined as vascular tortuosity and dilatation in at least 2 quadrants of the eye (International Committee for the Classification of Retinopathy of Prematurity 2005).

For the purposes of classifying a patient by ROP disease status, the worst eye ranked in descending order from worse to best in [Table 2-1](#) will be derived from the eCRF.

If both eyes have the same zone and stage, then the worst eye is the one with the greater total number of clock hours with the highest stage. If this is also the same for both eyes, then the left eye will be assigned as the worst eye.

The better-seeing eye and the worse-seeing eye at the 5th birthday visit are defined as the eye with a higher and lower ETDRS letter score, respectively. If both eyes have the same ETDRS letter score, then the left eye will be assigned as the worse-seeing eye.

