The best vision of the Low Visual Acuity Testing is defined as the best assessment with an answer 'YES', in the order of 'Count fingers' > 'Hand movement' > 'Light perception'. If all assessments have answers 'No', the best vision of the Low Visual Acuity Testing is defined as 'None of the above'. If the eye had a Low Visual Acuity Testing and all assessments have missing answers, the best vision of the Low Visual Acuity Testing is defined as 'Missing'.

Table 2-1 Ranking of Retinopathy of Prematurity Disease

Zone	Stage
Any	5
Any	4
I	AP-ROP
II	AP-ROP
I	3+
I	3
I	2+
I	1+
II	3+
II	2+
I	2
I	1
II	3
II	2
II	1+
II	1
III	3+
III	3
III	2+
III	2
III	1+
III	1

Abbreviations: AP-ROP - aggressive posterior retinopathy of prematurity; ROP - retinopathy of prematurity

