2.2.1.6 Missing post-baseline data

Observations with values ‘not done’, ‘not evaluable’, ‘not applicable’ will be treated as missing values.

Missing efficacy data will not be imputed.

Apart from AE and concomitant medication dates, missing post-baseline safety data will not be imputed.

Missing data for other variables will not be imputed unless otherwise specified.

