2.6 Analysis of the primary objective

2.6.1 Primary endpoint

The primary efficacy variable is the visual acuity (VA) in the better-seeing eye at the patient's fifth birthday as recorded by the investigator.

The primary efficacy analysis will be based on the Extension safety set.

Note that the ranibizumab 0.2 mg arm includes those patients that received ranibizumab 0.2 mg at baseline in the Core study. This includes patients that received laser treatment at a later date in either the Core or Extension study. Patients that permanently discontinue treatment with ranibizumab 0.2 mg are also included in primary efficacy analysis. However, patients for which the value of the primary variable is missing are excluded. A similar approach is taken for the ranibizumab 0.1 mg arm.

Similarly, the laser arm includes those patients that received laser at baseline in the Core study CRFB002H2301. This includes patients that received ranibizumab 0.2 mg treatment at a later date in either the Core or Extension study. Patients that permanently discontinue treatment with laser are also included in the primary efficacy analysis. However, patients for which the value of the primary variable is missing are excluded.

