2.6.4 Supportive analyses

The primary variable will also be assessed by using the randomized rather than the initial treatment received at baseline of Core study.

If a sufficient number of patients switch treatment during either the Core or Extension studies then additional analyses may be considered. This includes providing summary statistics for patients that receive monotherapy and on those that switch treatment separately.

If a sufficient number of patients receive a medication which prohibits further use of ranibizumab or study laser then an additional analysis will be conducted by performing the primary analysis (CMH test of [Section 2.6.2](#)) on the total Extension safety set including patients who received prohibited medications.

As a sensitivity analysis, the primary variable was also assessed separately for patients who had positive visual acuity letter score (excluding patients who have a 0 or missing visual acuity letter score).

As a sensitivity analysis, the primary variable was also assessed separately by best/worst eye.

The primary endpoint was also summarized by frequency of its value falling into several categories: 0 letter, ≥ 1 letter to ≤ 34 letters, ≥ 35 letters to ≤ 70 letters, and ≥ 71 letters.

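### Children with a low-vision test result but no letter score drop out of the primary analysis, and no supportive analysis brings them back into the arm comparison

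*SAP*

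**What the plan says.** **Who enters the primary.** SAP 2.2.1.6 sets the general rule: "Missing efficacy data will not be imputed". SAP 2.6.1 repeats for each arm that "patients for which the value of the primary variable is missing are excluded", and 2.6.3 confirms that "the analysis of the primary variable is only conducted for patients with a non-missing value of VA" at that visit.

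**Which eye is which.** The better- and worse-seeing eyes "are defined as the eye with a higher and lower ETDRS letter score, respectively" (2.2.1.1). The only special case is a tie: "If both eyes have the same ETDRS letter score, then the left eye will be assigned as the worse-seeing eye". Best and worst eye is a different ranking, by ROP disease. With equal zone and stage, "then the worst eye is the one with the greater total number of clock hours with the highest stage".

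**Low-vision testing.** SAP 2.2.1.1 orders the results from counting fingers down to none of the listed levels. It has a separate missing category, which begins "If the eye had a Low Visual Acuity Testing and all assessments have missing answers". SAP 2.8.1 tabulates these results by arm and by best/worst eye for children whose letter score is either 0 or missing. The plan therefore expects some low-vision results without a letter score.

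**Supportive analyses.** SAP 2.6.4 includes an analysis of positive scores only ("excluding patients who have a 0 or missing visual acuity letter score"), an analysis by best/worst eye, and a frequency table whose lowest class is 0 letters.

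**The concern.** Two children with the same very poor vision can be treated in opposite ways. If the site enters 0, the child counts at the floor of the scale. If the letter field is blank in both eyes and only the low-vision result is recorded, the child is excluded. The SAP does not say which entry a failed letter test produces.

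Where a blank reflects very poor vision, the value is missing because of the outcome, and the plan holds data showing this. Leaving such children out raises the arm mean. It distorts the ranibizumab-laser comparison if they are more frequent in one arm.

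There is a smaller gap in 2.2.1.1. With one scored eye there are not two letter scores to compare, so the programmer must decide whether the child enters and with which value. This matters mainly for the worse-seeing-eye endpoint.

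**Working it through.** The SAP gives no arm size, letter-score distribution or count of such eyes, so there is no stated figure to reproduce. The rules are compared first. The arithmetic after that is illustrative, and every input to it is assumed.

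**1. Does any 2.6.4 analysis include these children?**
- Positive scores only: no. It removes the recorded zeros as well.
- By best/worst eye: no. It still needs a letter score.
- Frequency table: no. It has no class for unscored low-vision children.
- By randomized treatment, by switching, or including prohibited medication: none of these addresses the missing score.

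**2. What can be inferred from other outputs?** Suppose the 2.8.1 low-vision table shows 4 best-eye and 4 worst-eye entries.
- The number of children unscored in both eyes can be anything from 0 to min(4, 4) = 4.
- The 0-letter row helps. Beside 60 other scored children, four recorded as 0 in both eyes give 4/64 = 6.25%, and four left blank give 0/60 = 0%.
- Comparing the analysed n with the Epoch 2 completers (2.4.1) helps further. However, completers may lack a score for other reasons, and the count also depends on how one-scored-eye children are handled.

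**3. Shift in one arm mean.** For n scored children with mean m and k low-vision-only children, the mean is m if the k are excluded and n × m/(n + k) if they are entered at 0.

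| n | m | k | Mean with zeros | Shift |
|---|---|---|---|---|
| 60 | 65 | 4 | 3900/64 = 60.9 | 4.1 |
| 60 | 50 | 4 | 3000/64 = 46.9 | 3.1 |
| 60 | 75 | 4 | 4500/64 = 70.3 | 4.7 |
| 40 | 65 | 4 | 2600/44 = 59.1 | 5.9 |
| 80 | 65 | 4 | 5200/84 = 61.9 | 3.1 |
| 60 | 65 | 1 | 3900/61 = 63.9 | 1.1 |
| 60 | 65 | 0 | 65.0 | 0 |

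**4. Shift in the arm difference.** Let scored children have the same mean m in both arms, and let qR and qL be the low-vision-only shares on ranibizumab and laser. Excluding these children gives a difference of 0. Entering them at 0 gives m × (qL − qR).
- 2% v 6%: 65 × 0.04 = 2.6 letters (2.2 at m = 55, 3.0 at m = 75).
- 2% v 10%: 65 × 0.08 = 5.2 letters (4.4 to 6.0 over the same range).
- 6% v 2%: −2.6 letters at m = 65.
- 5% v 5%: 0.

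**5. One scored eye.** Take an arm of 60 in which 4 children have one scored eye at 40 letters. The other 56 average 66 in the better eye and 58 in the worse.
- Better-seeing eye: 66.0 if the 4 are dropped; (56 × 66 + 4 × 40)/60 = 64.3 if kept.
- Worse-seeing eye: 58.0 if dropped; (56 × 58 + 4 × 40)/60 = 56.8 if the only scored eye is used; 56 × 58/60 = 54.1 if the unscored eye counts as 0.
- In a milder case, with 5% of children affected, a scored eye at 55 and a better-eye mean of 65, keeping them gives 0.95 × 65 + 0.05 × 55 = 64.5, against 65.0 if dropped.

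**The case against.** The exclusion rule is not a contradiction: 2.2.1.6, 2.6.1 and 2.6.3 agree. SAP 2.1 says the results have no valid inferential context, and under 2.6.2 the comparison is purely descriptive if the Core study's primary test was not significant. The SAP also expects recorded zeros, since it has a 0-letter class and an analysis that removes zeros. The recording rule may sit in procedures not shown here. If every failed letter test is entered as 0, nothing is lost. For one scored eye, the natural reading is that the scored eye is the better-seeing one and the worse-seeing value is missing.

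All of this stands and limits the weight of the point. It does not remove it. Section 2.8.1 explicitly allows for missing letter scores among children with low-vision results. Arm means, differences and confidence intervals will be reported whatever their inferential status.

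A reader might also infer that the planned outputs hide these children completely. The documents do not support that: the 0-letter row, the analysed n set against completers, and the by-arm low-vision table each give partial information. What is missing is a direct count and an analysis that includes them.

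**Conclusion.** The point holds as a gap that is cheap to close. As written, the plan can discard known very poor outcomes from the primary while keeping equivalent outcomes recorded as 0, and no supportive analysis tests the consequence.

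The size cannot be determined from the SAP. Under the assumptions above, an arm mean moves by 0 to about 6 letters and the arm difference by about −3 to +6. The effect on the difference is zero when the shares are equal, and there is no effect at all if failed tests are always recorded as 0. It would be wrong to conclude that the primary result is biased, because neither the number of such children nor the reason for their blanks is known.

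The one-scored-eye gap is minor. It is mostly missing detail with a natural reading, worth 1.7 letters on the better-seeing-eye mean in the harsher assumed case (66.0 − 64.3) and 0.5 in the milder one.

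**What to change.** 1. **SAP 2.6.4, sensitivity analysis.** Beside the as-recorded analysis, set an unscored eye with an answered low-vision test to 0 letters. The none-of-the-above result counts as answered; the missing category does not. Apply this to better- and worse-seeing-eye VA only when each eye has either a letter score or an answered low-vision test. A child with an eye that has neither result gets no floor-based value and is analysed as recorded; otherwise one low-vision eye beside an untested eye would wrongly give a better-seeing value of 0. The CMH code in 4.3 uses table scores, so 0 enters directly.
2. **Frequency table, by arm.** Add one row for children with no letter score in either eye but an answered low-vision test in both, and one row for other children with missing VA.
3. **SAP 2.2.1.1, one scored eye.** If the other eye has an answered low-vision test, the scored eye supplies the better-seeing-eye value, and the worse-seeing-eye letter score is missing in the as-recorded analysis. If the other eye has neither result, state whether the child is included and flag such children. This item fixes who enters the primary and should be acknowledged as doing so.

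The cost is a few sentences, one analysis and two table rows, with no new data. The downside is that some eyes unscored for non-visual reasons, such as poor cooperation, may be set to 0, which biases the other way, but only in the sensitivity analysis.

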2.6.4 Supportive analyses

The primary variable will also be assessed by using the randomized rather than the initial treatment received at baseline of Core study.

If a sufficient number of patients switch treatment during either the Core or Extension studies then additional analyses may be considered. This includes providing summary statistics for patients that receive monotherapy and on those that switch treatment separately.

If a sufficient number of patients receive a medication which prohibits further use of ranibizumab or study laser then an additional analysis will be conducted by performing the primary analysis (CMH test of [Section 2.6.2](#)) on the total Extension safety set including patients who received prohibited medications.

As a sensitivity analysis, the primary variable was also assessed separately for patients who had positive visual acuity letter score (excluding patients who have a 0 or missing visual acuity letter score).

As a sensitivity analysis, the primary variable was also assessed separately by best/worst eye.

The primary endpoint was also summarized by frequency of its value falling into several categories: 0 letter, ≥ 1 letter to ≤ 34 letters, ≥ 35 letters to ≤ 70 letters, and ≥ 71 letters.

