2.6.2 Statistical hypothesis, model, and method of analysis

If the primary hypothesis testing in the Core study shows statistical significance, the primary objective is to compare ranibizumab 0.2 mg versus laser with an informal testing as follows:

$$H_{01}: \mu_{\text{ranibizumab 0.2 mg}} - \mu_{\text{Laser}} = 0 \text{ versus } H_{A1}: \mu_{\text{ranibizumab 0.2 mg}} - \mu_{\text{Laser}} \neq 0$$

where $\mu_{\text{Treatment}}$ arm is the unknown mean VA in the better-seeing eye at the fifth birthday of patients in the relevant treatment arm.

The hypothesis will be tested by using stratified analysis of variance (ANOVA) using the Cochran-Mantel-Haenszel (CMH) test with the observed VA values (letters) as the ordinal response variable and the treatment arm as the factor (with levels ranibizumab 0.2 mg and laser). The effect of ROP zone at the baseline of the Core study is expected to have an effect at 5 years of age. Hence this variable is used as stratification factor in the analysis.

If the primary hypothesis testing in the Core study does not show statistical significance, only descriptive statistics (i.e., point estimate, and the 95% confidence interval) will be provided for the comparison between ranibizumab 0.2 mg and laser.

In addition, an unstratified two-way ANOVA using VA as the response variable and treatment arm and ROP zone as factors will be performed. This is essentially a one-way ANOVA using VA as the response variable and treatment arm as the factor, without ROP zone as the stratification factor. Two-sided 95% confidence intervals, assuming normality, will be produced for the VA within each treatment arm and the difference in VA between a pair of treatment arms will be calculated from least squares means. No p-values will be displayed for this analysis.

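### The supportive analysis on prohibited medications uses the same patients and data as the primary analysis, so it cannot show how those medications affect the visual acuity comparison

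*SAP*

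**What the plan says.** **Primary analysis.** Section 2.6.1 fixes the population: "The primary efficacy analysis will be based on the Extension safety set". Patients who later change treatment modality stay in their initial arm. For the 0.2 mg arm the section adds: "Patients that permanently discontinue treatment with ranibizumab 0.2 mg are also included in primary efficacy analysis". The 0.1 mg and laser arms are handled alike. The only removal is for a missing outcome: "However, patients for which the value of the primary variable is missing are excluded". Section 2.6.3 repeats this: "the analysis of the primary variable is only conducted for patients with a non-missing value of VA at the patient's fifth birthday visit".

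**Primary test.** Section 2.6.2 states: "The hypothesis will be tested by using stratified analysis of variance (ANOVA) using the Cochran-Mantel-Haenszel (CMH) test", stratified by ROP zone at Core baseline. This depends on the Core study. "If the primary hypothesis testing in the Core study does not show statistical significance, only descriptive statistics" are to be given for ranibizumab 0.2 mg versus laser.

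**Supportive analysis.** Section 2.6.4 takes effect once a sufficient number of patients have received a medication ruling out further study treatment. The method is the CMH test already named for the primary comparison, and the population is described as follows: "on the total Extension safety set including patients who received prohibited medications". The SAP does not say what number is sufficient.

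**The concern.** An additional analysis on the total set, with prohibited-medication patients put in, makes sense only as a contrast to a primary analysis that leaves them out. The current text has no such primary analysis, so the planned contrast compares a data set with itself.

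The risk is in interpretation. If the trigger is met, the report could present the output as supportive evidence that the VA comparison is robust to prohibited medications, although it could not have disagreed with the primary. The question behind the paragraph would stay unanswered, because no other analysis in the SAP commits to examining VA with these patients removed.

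**Working it through.** The SAP states no figure to reproduce. The check is whether the two inclusion rules, read from the current text, can select different patients or values.

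| Element | Primary analysis | Supportive analysis (2.6.4) |
|---|---|---|
| Set | Extension Safety Set (2.6.1) | Total Extension Safety Set |
| Exclusions from the set | Two consent deviations, INCL01 and WITH02 (Table 4-1) | The same, since it is the same set |
| Prohibited-medication patients | Not removed by any rule | Explicitly included |
| Treatment discontinuation or switch | Kept (2.6.1) | No different rule given |
| Missing VA | Not imputed, patient dropped (2.2.1.6, 2.6.3) | No different rule given |
| Endpoint and stratification | Better-seeing-eye VA, ROP zone | Same, by reference to 2.6.2 |
| Test | CMH test if the Core study was significant, otherwise descriptive | CMH test, no condition stated |

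**Step 1: could the set differ?** Section 2.3 defines the Extension Safety Set as Core Safety Set patients who enter the Extension, with no condition on medication. Table 4-1 lists only the two consent deviations. Section 2.4.1 names prohibited concomitant medication as a deviation category to be reported, not as a ground for exclusion. The sets are the same.

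**Step 2: could the data differ?** No section censors VA or sets it to missing after a prohibited medication. Section 2.2.2 keeps patients who stop study treatment under full assessment. The VA values are the same.

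**Step 3: could the statistic differ?** The statistic W* in Section 4.3 depends only on the VA scores, the arm and the zone of the included patients. With these unchanged, W* and its p-value are unchanged for any data. The difference is zero.

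**Step 4: the two branches of Section 2.6.2.**
- Core study significant: the primary reports the CMH test, and the supportive analysis returns the identical result.
- Core study not significant: the primary comparison gives a point estimate and 95% confidence interval. The supportive analysis then adds a CMH p-value from the same patients and values. This is a new number, but it says nothing about prohibited medications, and it supplies a test that Section 2.6.2 withholds in that branch.

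**Illustration (all inputs assumed, none from the SAP).** One data set was simulated with 60 patients per arm, each with a 15% chance of missing VA and a 10% chance of prohibited medication.
- Primary rule: n = 93, CMH statistic 0.000134, p = 0.9908.
- Supportive rule as written: the same 93 patients, 0.000134, p = 0.9908.
- Excluding prohibited-medication patients: n = 82 (93 − 82 = 11 removed), 0.000216, p = 0.9883.

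The simulation gave prohibited medication no effect on VA, so the small change in the third line says nothing about this trial. It shows only that a different result requires a different set of patients or data.

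**The case against.** The overlap of patients and data is hard to dispute, but several limits apply.

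- **Not always a duplicate.** A reader might infer that the supportive result must always repeat the primary result. Section 2.6.2 does not support that: if the Core study was not significant, the primary comparison has no CMH p-value to repeat. This stands. What holds in both branches is that the patients and data are the same.
- **May never be run.** The analysis depends on a sufficient number of patients, so a reader should not assume that the table will appear. This stands, and the undefined trigger is a weakness of the same sentence.
- **Related content exists.** Section 2.6.4 foresees separate summaries for monotherapy and switched patients, and Section 2.5.2 allows therapies that rule out further study treatment to be summarised separately. Both are optional, and neither re-analyses VA without these patients. This stands only in part.
- **Little is at stake for the primary result.** Section 2.1 disclaims type I error control, and Section 2.6.2 calls the testing informal. A redundant supportive analysis cannot bias the primary estimate. This stands and keeps the point at moderate weight.
- **Exclusion has its own cost.** Removing patients because of treatment received after baseline, probably linked to worse disease, can bias the comparison between arms. This stands, so deleting the sentence is an equally legitimate correction.

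**Conclusion.** The point holds in this form: under the written rules the Section 2.6.4 analysis uses the same patients and VA data as the primary and cannot show how prohibited medications affect the comparison. The difference is zero wherever the primary CMH test is run. Otherwise the analysis adds only a p-value on unchanged data.

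A reader might also want to say how many letters a real exclusion analysis would move the result. The SAP does not support any such figure. It gives neither the share of patients on these medications nor their VA. An assumed shift in one arm's mean would also not be the shift in the treatment difference, because similar use in both arms would largely cancel.

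The conclusion rests on the current text of Sections 2.2.1.6, 2.3, 2.6.1 to 2.6.4 and Table 4-1. The amendment log records that Amendment 3 stopped excluding data after such treatments, so the sentence may be a leftover. That is background only, and the finding does not depend on it. The change should be made, but the primary analysis itself is unaffected.

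**What to change.** Choose one of two corrections to Section 2.6.4.

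1. **Replace the sentence** with a sensitivity analysis that repeats the primary analysis on the Extension Safety Set, excluding patients who received a medication ruling out further ranibizumab or study laser before their fifth-birthday VA assessment. State that:
   - it is shown beside the primary analysis;
   - it follows the same Core-study condition on testing as Section 2.6.2;
   - it is run when a stated number of such patients is reached;
   - it conditions on a post-baseline event and may therefore be biased.
2. **Delete the sentence**, so that a duplicate is not reported as supportive evidence.

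The first option costs a few lines of SAP text and one informative table in place of a redundant one. The second costs one deletion. Neither changes the primary analysis or the conduct of the trial.
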